9.4 Statistical analyses

The statistical analyses will be performed by Parexel or other designated third-party providers, under the direction of the Biostatistics Group, AstraZeneca. Further detail will be provided in the Statistical Analysis Plan (SAP).

Data from each part/module will be presented separately. All patients who undergo intra-patient dose escalation will be analysed & reported as per their starting dose.

Methods common to all modules are detailed below.

Demographic Data

Characteristics of the patients, including medical history and disease characteristics at baseline will be listed for each patient and summarised by cohort.

Reasons for discontinuation of study treatment will be listed including the study day of treatment discontinuation and will be summarised by cohort.

Exposure

Exposure to each study treatment, ie, total amount of study treatment received will be listed for all patients.

Total treatment duration (=date of last dose minus date of first dose + 1) and actual treatment duration (=total treatment duration excluding dose interruptions not in accordance with the protocol) will be summarised for each study treatment and cohort by the following: mean, standard deviation, minimum, maximum, median, and number of observations. In addition, the number and percentage of patients with at least 1 non-protocolled dose interruption and at least 1 dose reduction will be presented separately for the initial period of evaluability defined as 28 days and for any time following this initial period of the study.

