9.4.2 Safety analyses

These are primary variables.

All safety analyses will be performed on the safety analysis set. All patients who receive at least 1 dose of study treatment will be included in the assessment of the safety profile. At the end of the study, appropriate summaries of all safety data will be produced, as defined below.

Data from all cycles of initial treatment will be combined in the presentation of safety data. AEs will be listed individually by patient and cohort. For patients who have a dose modification, all AEs (due to drug or otherwise) will be assigned to the initial dose group. The number of patients experiencing each AE will be summarised by the Medical Dictionary for Regulatory Activities (MedDRA) system organ class, MedDRA preferred term and CTCAE grade. The number and percentage of patients with AEs in different categories (eg, causally related, CTCAE Grade \geq 3 etc) will be summarised by dose regimen, and events in each category will be further summarised by MedDRA system organ class and preferred term, by dose group. SAEs will be summarised separately.

Any AE occurring before the first dose of study treatment (ie, before study Day 1) will be included in the data listings but will not be included in the summary tables of AEs. Treatment-emergent AEs occurring prior to first dose of investigational product (ie, before study Day 1) which subsequently worsen in severity following dosing will be included in the summary tables.

Any AE occurring within the defined 28-day follow-up period after discontinuation of study treatment will be included in the AE summaries. Any AEs in this period that occur after a patient has received further therapy for cancer (following discontinuation of study treatment) will be flagged in the data listings. AEs occurring after the 28-day follow-up period after discontinuation of study treatment will be listed separately, but not included in the summaries.

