 - If there is more than one value per patient within a time window then the closest value to the scheduled visit date should be summarised, or the earlier, in the event the values are equidistant from the nominal visit date. The listings should highlight the value for the patient that contributed to the summary table, wherever feasible. Note: in summaries of extreme values, all post baseline values collected are used including those collected at unscheduled visits regardless of whether or not the value is closest to the scheduled visit date
- For summaries at a patient level, all values should be included, regardless of whether they appear in a corresponding visit-based summary, when deriving a patient level statistic such as a maximum.

Table 4: Visit windowing (safety analysis)

Cycle	Target Day	Analysis visit	Analysis Visit Window
	screening	Baseline	Day -28 to Cycle 0 Day 1 (pre-dose)
C0	Day 1 (pre-dose)		No analysis visit window: First day of intake of AZD7648

C0	Day 2	Cycle 0 Day 2	C0D1 + 1 day
C0	Day 3	Cycle 0 Day 3	C0D1 + 2 days
C0	Day 4	Cycle 0 Day 4	C0D1 + 3 days
C1	Day 1	Cycle 1 Day 1	No analysis visit window: Monotherapy: First day of restart of AZD7648 after C0 Combinations: Day 1 of associated anticancer agent or first day of restart of AZD7648 after C0 whichever comes first
C1	Day Y	Cycle 1 Day Y	If Y=3 then Day 2 to Day 4 If Y=7 then Day 2 to Day 7
C1	Day 8	Cycle 1 Day 8	^a Last day of previous interval + 1 day to Day 11
C1	Day 15	Cycle 1 Day 15	Day 12 to Day 18
C1	Day 22	Cycle 1 Day 22	Day 19 to C2D1 – 2 days if following cycle Otherwise Day 19 to C1D1+26 days (last cycle)
C2	Day 1	Cycle 2 Day 1	From: Monotherapy: C1D1 + 28 – 1 day or (first day of intake of AZD7648 after C1D1+28) - 1 day; if AZD7648 is off on C1D1+28-1 day. Combinations: (Day 1 of associated anticancer agent for C2 or C1D1 + 28) – 1 day; if associated anticancer agent stopped;

			
or
 
(first day of intake of associated anticancer agent after C1D1+28) – 1 day; if associated anticancer agent is off since C1D1+28-1 day
 
To:
 
Monotherapy: C1D1 + 28 + 1 day
 
or
 
(first day of intake of AZD7648 after C1D1+28) +1 day if AZD7648 is off on C1D1+28-1 day
 
Combinations: (Day 1 of associated anticancer agent for C2 or C1D1 + 28) +1 day; if associated anticancer agent stopped.
 
or
 
(first day of intake of associated anticancer agent C1D1+28) +1 day; if associated anticancer agent and off on C1D1+28-1 day.

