3.2.1.7 Laboratory Data

All laboratory results collected will be listed.

Summaries for safety laboratory will only include the parameters specified in [Table 6](#).

All values will be classified as low (below range), normal (within range), or high (above range) based on local laboratory reference ranges. Results will be converted to standard units and graded with CTCAE version 5.0. A shift table from baseline to maximum value will be summarised for urinalysis variables. Maximum post-baseline CTC grade will also be calculated.

If the same parameter is found as measured in serum and in plasma, then the summaries will not distinguish between them (e.g. values from plasma albumin and serum albumin will be summarised under albumin). If the same parameter is found as measured in serum and in plasma within the same patient, which would be a rare case, then the change from baseline will only be calculated for those post-baseline values using the same source, i.e., only within plasma or serum. If one patient has multiple toxicity grades, because they are derived separately from serum and plasma then the maximum value of the two will be considered.

For all continuous laboratory assessments, absolute value, change from baseline and percentage change from baseline will be summarised using descriptive statistics at each scheduled assessment time by actual treatment group.

For clinical chemistry and haematology, shift tables will present movements from baseline to worst value on-treatment (defined from start of treatment to biopsy day) according to reference range classification. CTCAE grade changes from baseline to on-treatment will also be provided. Corresponding shift tables (“Negative”, “Trace”, “Positive”, “0”, “+”, “++”, “+++”) will be produced for urinalysis. In addition, the number of patients with ≥ 2 CTCAE grade changes and CTCAE grade changes to 3 or 4 will be summarised by actual treatment group for clinical chemistry and haematology parameters.

Plots for both maximum post-baseline alanine transaminase (ALT) and aspartate transaminase (AST) versus the maximum post-baseline total bilirubin (expressed as multiples of their upper limit of normal [ULN] reference range) will be produced with reference lines at 3 x ULN for ALT and AST and 2 x ULN for total bilirubin. Spaghetti plots of absolute values and change from baseline values for all haematology and clinical chemistry parameters will also be presented.

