3.2.1.11 ECG

All ECG data received will be presented in data listings.

Absolute values, changes from baseline and percentage change from baseline to each scheduled visit will be summarised by module, by part, by cohort and visit for the following ECG variables: heart rate, QT interval corrected for heart rate using Fridericia's formula (QTcF), RR, PR, QRS, and QT. The average of the three individual tracings will be used in summaries. However, the individual tracings will be displayed in the data listings.

Number and percentage of patients with QTcF results in each of the following categories will be summarised:

- greater than AstraZeneca Cardiac SKG upper reference range at any time on treatment.
- absolute value > 450 msec.
- absolute value > 480 msec.
- absolute value > 500 msec.
- change from baseline > 30 msec.
- change from baseline > 60 msec.
- absolute value > 450 msec and change from baseline > 30 msec.
- absolute value > 500 msec and change from baseline > 60 msec.

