3.2.2.1.2 Best objective response

Best objective response (BoR) is calculated based on the overall visit responses from each RECIST 1.1 assessment. (see Section 3.2.2.1.1). It is the best response a patient has had following first dose of study treatment on cycle 1, day 1; but prior to starting any subsequent cancer therapy or up to and including RECIST progression or the last evaluable assessment in the absence of RECIST progression. Categorisation of BoR will be based on RECIST 1.1 using the following response categories: CR, PR, SD, PD and NE.

The confirmation of CR or PR should be performed at the next RECIST assessment and must not be less than 4 weeks later. For determination of a best response of SD, the earliest of the dates contributing towards an overall visit assessment will be used. SD should be recorded at least 8 weeks minus 1 week (to allow for an early assessment within the assessment window), after first dose/administration of study medication at cycle 1. For CR/PR, the initial overall visit assessment which showed a response will use the latest of the dates contributing towards an overall visit assessment.

It will be determined programmatically based on RECIST using all site investigator data up until the first progression event. The denominator will be consistent with that used in the ORR analysis for the respective analysis set.

For patients whose progression event is death, BoR will be calculated based upon all evaluable RECIST assessments prior to death. For patients who die with no evaluable RECIST assessments post-baseline, if the death occurs ≤ 17 weeks (i.e., 16 weeks + 1 week to allow for a late assessment within the assessment window) after first dose/administration of study medication at cycle 1, day 1, then BoR will be assigned to the progression (PD) category. For patients who die with no evaluable RECIST assessments, if the death occurs > 17 weeks after start of treatment at cycle 1 then BoR will be assigned to the NE category.

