- All analyses will be performed on data collected before intra-patient dose escalation, if any. Data collected after dose escalation will be presented in listings only and will be flagged. The actual dose at the time of the assessment will be presented in the listings.
- Additional sensitivity analysis might be performed on a subset of patients without important protocol deviations if needed.

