Any AE occurring within the defined 28 days follow-up period after discontinuation of investigational product will be included in the AE summaries. Any adverse events in this period that occur after a patient has received further therapy for cancer (following discontinuation of investigational product) will be flagged in the data listings. TEAEs occurring prior to first dose of investigational product (ie, before study Day 1) which subsequently worsen in severity following dosing will be presented in the summary tables. All other AEs occurring prior to first dose of investigational product (ie, before study Day 1), or after the 28 days follow-up period after discontinuation of investigational product will be listed separately, but not included in the summaries.

Fluctuations observed in CTCAE grades during study will be listed (where collected). When assigning a maximum CTCAE grade to a TEAE, only grade changes occurring after the date of first dose of study treatment and up to 28 days after the last dose of study treatment will be considered.

Details of any deaths will be listed for all patients.

Haematology and clinical chemistry results will be summarised using descriptive statistics (mean, median, standard deviation, minimum, maximum and number of observations). For all laboratory variables included in the current version of CTCAE, the CTCAE grade will be summarised. The post-baseline results and its change from baseline for laboratory, ECG, vital signs data at each timepoint will be summarised. For all haematology and clinical chemistry results, change from baseline will be plotted using a spaghetti plot. Creatinine clearance and echocardiogram (LVEF) results at different timepoints and their change from baseline will be summarised using descriptive statistics. Creatinine clearance and echocardiogram (LVEF) results will be listed as well by visit. LVEF will also be summarised by categories listed in section 3.2.1.12. All abnormal findings from the physical exam will be listed. The number of patients for each ECOG-PS grade will be presented.

For the core module, individual 4 β -hydroxy cholesterol concentration data will be listed only.

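### SAP 4.1 drops all data after intra-patient dose escalation from every analysis, an undeclared departure from the protocol that conflicts with the SAP's own safety and response rules

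*SAP*

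**What the plan says.** SAP 4.1 sets a rule for the whole study: "All analyses will be performed on data collected before intra-patient dose escalation, if any". Anything collected later is listed and flagged, with the actual dose shown, but not summarised.

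The protocol handles the same patients differently. Section 9.4: "All patients who undergo intra-patient dose escalation will be analysed & reported as per their starting dose". Section 9.4.2, on safety: "For patients who have a dose modification, all AEs (due to drug or otherwise) will be assigned to the initial dose group".

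SAP Section 6, which lists changes from the protocol, covers only PK symbols and additional PK parameters. The SAP version history does not mention the cut either.

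Elsewhere the SAP has inclusion rules with no exception for escalation:

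- AEs (4.2.1): "Any AE occurring within the defined 28 days follow-up period after discontinuation of investigational product will be included in the AE summaries".
- Extreme values (3.1): "in summaries of extreme values, all post baseline values collected are used including those collected at unscheduled visits".
- Laboratory grades (3.2.1.7): "Maximum post-baseline CTC grade will also be calculated".
- QTcF (3.2.1.11), first category: "greater than AstraZeneca Cardiac SKG upper reference range at any time on treatment".
- Best objective response (3.2.2.1.2): "It will be determined programmatically based on RECIST using all site investigator data up until the first progression event".
- Objective response (3.2.2.1.3) counts at any time before progression or subsequent therapy, and best tumour change (3.2.2.1.5) draws on every post-baseline assessment.

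The exposure and PFS sections (3.2.1.1 and 3.2.2.1.6) do not mention escalation. They give no end date or censoring rule through which the cut could be applied.

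**The concern.** Safety is the primary objective, and SAP 1.1 says the outputs were reduced to focus mainly on it. Under the 4.1 rule, AEs, SAEs, AE-related discontinuations and the worst laboratory, vital sign and ECG values seen after escalation leave the summary tables for Core Module patients. Protocol 4.1.2 allows escalation so that patients can move off low starting doses, and 6.1.2 sets no limit on the number of escalations. One patient's experience at several higher doses can therefore be absent from every summary.

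Response is affected too. Escalation follows a scheduled scan, so a response first seen at that scan would usually lose its confirmation, although the patient still counts in the ORR denominator.

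**Working it through.** **1. The rules side by side**

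| Item | SAP 4.1 | Other rule |
|---|---|---|
| Escalated patients | Data before escalation only | Reported under starting dose (protocol 9.4) |
| AEs after a dose change | Listings only | All assigned to the initial dose group (protocol 9.4.2) |
| AEs in the 28 days after discontinuation | Listings only if escalated | In the summaries (SAP 4.2.1) |
| Extreme values | Before escalation only | All post-baseline values (SAP 3.1) |
| Best response | Before escalation only | All data to first progression (SAP 3.2.2.1.2) |

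The third row is the sharpest clash. A patient who escalates discontinues after escalating, so that patient's whole 28-day follow-up is post-escalation data. One rule includes those AEs and the other removes them.

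**2. Direction.** The cut removes events but not patients. Escalated patients stay in the safety set (SAP 2.2), and percentages use the analysis-set total (SAP 4.1). AE incidence can only fall or stay the same.

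**3. Incidence per cohort.** Protocol 6.1.2 allows single-patient cohorts, then 3 to 6 patients. If a cohort's only event in a category occurs after escalation:

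- n = 1: 1/1 = 100% becomes 0%
- n = 3: 1/3 = 33.3% becomes 0%
- n = 6: 1/6 = 16.7% becomes 0%

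**4. Share of treatment cycles left in listings only.** With c cycles before the cut and T in total, the share is max(0, T − c)/T. The values of T are assumptions.

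| Escalated at | T = 4 | T = 6 | T = 12 |
|---|---|---|---|
| Cycle 3 Day 1 (c = 2) | 50% | 67% | 83% |
| Cycle 5 Day 1 (c = 4) | 0% | 33% | 67% |

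**5. Can a response be confirmed before the cut?** Inputs: 28-day cycles; scans every 8 weeks ± 1 week from Cycle 1 Day 1; escalation on the Day 1 following a scheduled scan (protocol 6.1.2); confirmation at least 4 weeks later (SAP 3.2.2.1.2 and 3.2.2.1.3). With Cycle 1 Day 1 as day 1, cycle Day 1s fall on 1 + 28j and scan k on 1 + 56k ± 7.

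| Scan k | Scan days | Directly following Day 1 | Next scheduled scan |
|---|---|---|---|
| 1 | 50–64 | 57 or 85 | 106–120 |
| 2 | 106–120 | 113 or 141 | 162–176 |
| 3 | 162–176 | 169 or 197 | 218–232 |

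The cut comes 0 to 28 days after the scan, and the next scheduled scan is later still. For scan 1 on day 50, 57 or 64, the earliest confirmation is day 78, 85 or 92. A response first seen at scan k is therefore confirmable on scheduled scans only if escalation waits until after scan k + 1. The one exception is a gap of 28 days (slightly more with the ± 2 day visit window) with an extra scan before the dose change.

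**6. Effect on ORR if a cohort's only response is lost this way.** SAP 4.2.2 specifies Clopper-Pearson 80% intervals, so each tail is 0.10.

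- 1/3 = 33.3%: lower limit 1 − 0.9^(1/3) = 3.5%; upper limit solves (1 − p)³ + 3p(1 − p)² = 0.10, giving 80.4%.
- 0/3 = 0%: upper limit 1 − 0.1^(1/3) = 53.6%.
- 1/6 = 16.7%: lower limit 1 − 0.9^(1/6) = 1.7%; upper limit solves (1 − p)⁶ + 6p(1 − p)⁵ = 0.10, giving 51.0%.
- 0/6 = 0%: upper limit 1 − 0.1^(1/6) = 31.9%.

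**7. Outside the problem.** Both documents treat escalated patients as not evaluable for DLT at the higher dose. Protocol 8.5 confines intra-patient escalation to the Core Module.

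**The case against.** The best defence is that 4.1 is an overarching data cut within which the later rules operate, and that the protocol is less explicit than it looks. Protocol 9.4 says which dose a patient is reported under, not how long data are counted. Protocol 9.4.2 speaks of dose modification. Section 6.6, under that title, refers escalation to Section 6.1.2, and its Table 7 lists only reductions. Both documents also speak of combining all cycles of initial treatment, which could mean treatment before escalation.

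This does not rescue the rule. Protocol 9.4 names intra-patient escalation and nowhere drops data. The initial-treatment phrase is undefined, and protocol 9.4.2 uses it in the same paragraph that keeps all AEs after a dose modification. Giving 4.1 precedence would settle the internal conflict but leave an undeclared change that can only lower AE incidence.

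Some points stand:

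- Placing higher-dose events under a low starting dose is a real drawback in a dose-finding study.
- The chemistry and haematology shift tables stop at a biopsy day (SAP 3.2.1.7). If that means the Cycle 1 biopsy, the cut removes nothing from them. Maximum CTC grade and the ALT/AST-against-bilirubin plots do not have that limit.
- SAP 4.1 restricts descriptive statistics to n of at least 3, so the one-patient percentage may never be tabulated.
- Share of cycles is not share of events, and the ORR figures describe a specific case.
- Development has been halted, and the excluded data remain in the listings. Deaths are listed for all patients.

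**Conclusion.** The concern holds. SAP 4.1 departs from protocol 9.4 and 9.4.2 without declaring it, and it conflicts with the SAP's own rules for AEs, extreme values, best response, ORR and best tumour change. The total effect cannot be computed, because the documents do not give the number of patients escalated and it could be zero.

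The per-cohort figures are conditional: they assume that a cohort's only event, or only response, is the one removed. A response already confirmed before escalation is kept. The effect on PFS is unknown, because the SAP does not say how the cut would be applied there. This should be fixed before the tables are programmed. Confidence is high that the text is wrong as written.

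**What to change.** Replace the sentence in SAP 4.1 with rules by endpoint:

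- **All data, reported under the starting dose:** AEs, SAEs, AE-related discontinuations, exposure, worst-value and maximum-grade laboratory summaries (including liver), vital signs and ECG extremes, best tumour change, best objective response, ORR, duration of response and PFS.
- **Pre-escalation data only:** PK and by-visit means. This limited cut still departs from protocol 9.4, so declare it in SAP Section 6.
- **One supplementary AE table**, by actual dose at onset or restricted to pre-escalation events. It meets the legitimate aim of not attributing higher-dose events to the starting dose.

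The cost is SAP wording plus one table. No new data are needed, because 4.1 already puts actual dose in the listings. The downside is that some higher-dose events appear under the starting dose in the main table; the supplementary table makes that visible.

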4.2 Description of Analysis methods

In general, summaries will be split by modules/parts/Cohorts and doses.

4.2.1 Demographic, Dosing, and Safety and Tolerability data

There is no formal statistical analysis of safety and tolerability data required for this study. Demographic and other baseline disease characteristics, important protocol deviations, concomitant medication, dosing, exposure, safety, tolerability and DLT data will be listed and tabulated and summarised as defined by the current AZ standards (Oncology early phase study outputs).

Exposure

Exposure to investigational product i.e., total amount of study drug received will be listed for all patients.

Actual and total treatment duration will be summarised by the following: mean, standard deviation, minimum, maximum, median and number of observations. In addition, the number and percentage of patients with at least one dose interruption and at least one dose reduction will be presented separately for the initial period of evaluability defined as 28 days and for any time following this initial period of the study. The number of treatment cycles received by patients will be summarised.

Exposure plots will be produced, with a line presented for each patient in the study. Dose intensity data will be summarised using medians, and quartiles as well as the minimum and maximum values.

Safety

Data from all cycles of initial treatment will be combined in the presentation of safety data.

An overall summary table of the number of patients experiencing each category of adverse event will be produced.

The number of patients experiencing treatment emergent adverse events by MedDRA system organ class (SOC) and MedDRA preferred term (PT) will be presented, with further splits by CTCAE grade, causal relationship to study medication and adverse events classed as Grade 3 or higher.

Separate tables will present dose limiting toxicities, adverse events leading to discontinuation, serious adverse events and other significant adverse events. All AE data will be listed appropriately.

Any AE occurring within the defined 28 days follow-up period after discontinuation of investigational product will be included in the AE summaries. Any adverse events in this period that occur after a patient has received further therapy for cancer (following discontinuation of investigational product) will be flagged in the data listings. TEAEs occurring prior to first dose of investigational product (ie, before study Day 1) which subsequently worsen in severity following dosing will be presented in the summary tables. All other AEs occurring prior to first dose of investigational product (ie, before study Day 1), or after the 28 days follow-up period after discontinuation of investigational product will be listed separately, but not included in the summaries.

Fluctuations observed in CTCAE grades during study will be listed (where collected). When assigning a maximum CTCAE grade to a TEAE, only grade changes occurring after the date of first dose of study treatment and up to 28 days after the last dose of study treatment will be considered.

Details of any deaths will be listed for all patients.

Haematology and clinical chemistry results will be summarised using descriptive statistics (mean, median, standard deviation, minimum, maximum and number of observations). For all laboratory variables included in the current version of CTCAE, the CTCAE grade will be summarised. The post-baseline results and its change from baseline for laboratory, ECG, vital signs data at each timepoint will be summarised. For all haematology and clinical chemistry results, change from baseline will be plotted using a spaghetti plot. Creatinine clearance and echocardiogram (LVEF) results at different timepoints and their change from baseline will be summarised using descriptive statistics. Creatinine clearance and echocardiogram (LVEF) results will be listed as well by visit. LVEF will also be summarised by categories listed in section 3.2.1.12. All abnormal findings from the physical exam will be listed. The number of patients for each ECOG-PS grade will be presented.

For the core module, individual 4 β -hydroxy cholesterol concentration data will be listed only.

